13.1 CRITERIA FOR REMOVAL FROM STUDY

13.2 *Group 1* patients come off study if progressive disease develops at any time after cycle 1. (see section 12.2).

13.3 *Group 2* patients come off study if progressive disease develops at any time after cycle 1 (see section 12.3).

13.4 Life-threatening grade 4 toxicity clearly attributable to 3F8.

13.5 The investigators will make every reasonable effort to keep each patient in the study until all planned treatments and assessments have been performed. The investigators may discontinue study drug treatment for the following reasons:

- **Adverse events**, including unacceptable toxicity or exacerbation of underlying disease, associated with study drug administration and necessitating discontinuation of treatment. Patients who are removed from the study due to adverse events will be treated and followed according to established, acceptable medical practice. All pertinent information concerning the outcome of such treatment will be entered in the Case Report Form or on the Serious Event Report, as applicable.

- **Withdrawal of consent.** The patient's desire to withdraw from the study may occur at any time. The investigator should carefully consider whether the patient's withdrawal of consent is due to an adverse event, and if so, record the adverse event as the reason for withdrawal.
- **Withdrawal by the physician** for clinical reasons not related to study drug treatment, for example, clinical need to administer a concomitant medication that is excluded by the protocol, in the absence of an adverse event.
- **Violation of the study protocol**, including failure to return for required treatments or assessments. Patients who fail to return for treatments will be withdrawn from the study if more than 4 scheduled doses are missed

13.6 Patients will not be removed from study in order to receive radiotherapy.

subjects, 18 will be accrued during stage 1 and 15 during stage 2. The trial stops early if none of the first 18 patients survive for two years without relapse. Otherwise, the trial continues until 33 patients are accrued. Treatment will be considered promising if two or more patients experience two-year relapse-free survival and accrual can continue up to 50 patients with the goal of strengthening the findings

* Patients with prior antibody treatment or immunotherapy are less common and so only a trial with lower power is feasible. We will accrue 19 patients, declaring treatment as promising if two or more experience two-year relapse-free survival. This design has a power of 80% and an alpha of 5%, a null hypothesis of 1% and an alternate hypothesis of 15%. Only a one-stage design is feasible with these characteristics as an observed zero response rate would be consistent with a true response rate of 15% for an interim analysis conducted at all possible stopping points up to the 18th patient. If the findings are favorable, accrual can increase to 35, with the aim of strengthening the conclusions.

* Patients who went off protocol to receive therapy for relapse in the central nervous system, or to receive additional chemotherapy because of HAMA (section 9.1), are not included in the statistical analyses for these groups.

Utility of RT-PCR: The association between histologic examination and real time RT-PCR regarding BM status can be assessed by the Wilcoxon statistic. The clinical significance (relapse-free survival) of histologic results and real time RT-PCR findings in both groups can be assessed by log-rank test or Cox regression model or time dependent Cox regression model.

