9.1 TREATMENT/INTERVENTION PLAN

9.2 **Schedule:** The total dosage of 3F8 per cycle is the same as in prior trials (100 mg/m²), administered at 20 mg/m²/day and infused over ~1.5 hr or less (0.5 hr is customary), with analgesics and antihistamines used as needed for expected side-effects. 3F8 is started ~1 hr after completion of GM-CSF administration. GM-CSF is dosed at 250 mcg/m²/day from day -5 to day +1 (Wednesday to Tuesday is customary), and is 500 mcg/m²/day thereafter (i.e., on days +2 to +4; Wednesday to Friday), as in the predecessor protocol.^{18,74} Patients come off study if progressive disease occurs or if there is life-threatening grade 4 toxicity from 3F8; otherwise, patients will receive a minimum of 4 cycles of treatment and will continue treatment through 24 months. It is expected that patients will receive ~10 cycles.

For **Group 1** patients (enrolled on study for treatment of primary refractory disease), the break between end of a cycle of 3F8/GM-CSF and start of next cycle is 2-to-4-weeks through 4 cycles after achievement of CR in BM; subsequent breaks are ~8 weeks. In this group, isotretinoin is started after documentation of response to, and after ≥2 cycles of, 3F8/GM-CSF. Road map/schema is in section 4.2.

For **Group 2** patients (enrolled on study in CR/VGPR, i.e., with no evidence of disease), the break between end of a cycle and start of next cycle is 2-to-4 weeks through 4 cycles;

subsequent breaks are ~8 weeks. Isotretinoin is started after cycle 2 of 3F8/GM-CSF. Road map/schema is in section 4.2. Regarding patients in second or greater CR from relapse in the central nervous system, if they develop early HAMA which precludes timely completion of the minimum of 4 cycles of 3F8/GM-CSF, they are eligible to go off protocol, to be treated with low-dose maintenance regimens of irinotecan,⁹⁴ temozolomide,⁹⁵ or the two agents combined;⁹⁶ they can resume treatment with 3F8/GM-CSF if HAMA becomes negative.

Patients who develop early HAMA which precludes timely treatments with 3F8/GM-CSF (>4 week delay) are eligible to receive low-dose maintenance regimens such as irinotecan alone,⁹⁴ temozolomide alone,⁹⁵ irinotecan-temozolomide,⁹⁶ or cyclophosphamide-topotecan.⁹⁷ They can also receive anti-HAMA agents such as rituximab and cyclophosphamide. They resume treatment with 3F8/GM-CSF if HAMA becomes negative.

9.3 3F8/GM-CSF treatment schedule (one cycle).

Days -5 to -1: GM-CSF 250 mcg/m²/day, subcutaneously.

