12.1 CRITERIA FOR THERAPEUTIC RESPONSE/OUTCOME ASSESSMENT

12.2 Response duration is calculated from first day of treatment with 3F8.

12.3 *Group 1* patients (i.e., patients treated for primary refractory disease) are considered a treatment failure under this protocol if progressive disease develops.

12.4 *Group 2* patients (i.e., patients in CR/VGPR) are considered a treatment failure under this protocol if progressive disease develops.

12.5 Disease status is defined by the International Neuroblastoma Response Criteria,⁹¹ supplemented by RT-PCR findings in bone marrow (section 8.6)

- Complete response/remission (CR): no evidence of disease.
- Very good partial response/remission (VGPR): >90% decrease in all disease parameters, except bone scan unchanged or improved; bone marrow must be free of disease.
- Partial response/remission: >50% decrease in all disease parameters, except bone scan unchanged or improved; no more than 1 positive bone marrow site.
- Mixed response: >50% decrease in ≥ 1 but not all disease markers.
- Stable disease: <50% decrease in all tumor markers.
- Progressive disease: new lesion, or >25 % increase in any disease marker.

12.6 Adequacy of trial: All patients who fulfill the eligibility requirements and receive a first dose of 3F8 will have an adequate trial.

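### Section 14 leaves out of the second-or-later-remission analyses patients who went off protocol for CNS-relapse therapy; this conflicts with 12.6 on any reading and, read literally, discards relapse events

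*Combined protocol and SAP*

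**What the plan says.** Section 14.0 sets out two designs for patients treated in second or later remission: a two-stage design (18 then 15 patients) for those without prior antibody or immunotherapy, and a one-stage design of 19 patients for those with it. Both call the treatment promising if at least two patients are relapse-free at two years. A third bullet then names two kinds of patient. The first are "Patients who went off protocol to receive therapy for relapse in the central nervous system". The second are those who left for chemotherapy on account of HAMA, with a reference to section 9.1. Of both kinds the bullet says that they "are not included in the statistical analyses for these groups".

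Three other places bear on this sentence.

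- Section 12.4 says that Group 2 patients "are considered a treatment failure under this protocol if progressive disease develops". Section 12.5 counts a new lesion as progressive disease.
- Section 12.6 says: "All patients who fulfill the eligibility requirements and receive a first dose of 3F8 will have an adequate trial".
- Section 9.2, under heading 9.1, is the only other text that links CNS relapse with leaving protocol. It begins "Regarding patients in second or greater CR from relapse in the central nervous system, if they develop early HAMA which precludes timely completion"; what cannot be completed in time is the four-cycle minimum. For such patients it then allows that "they are eligible to go off protocol, to be treated with low-dose maintenance regimens". They may return to 3F8/GM-CSF if HAMA becomes negative.

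**The concern.** The endpoint in these cohorts is being relapse-free at two years. A CNS relapse on study is a new lesion, so it is progressive disease and a treatment failure. If that patient then leaves protocol for CNS therapy, the sentence in section 14 takes the patient out of the analysis. The outcome event would itself cause the exclusion, and only failures would be lost.

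The group in 9.2 is different. Those patients had their CNS relapse before enrolment, entered in remission, and left because of HAMA. Dropping them is a selection made after enrolment, on a ground that may be related to prognosis, and some of them may be relapse-free at two years.

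An analyst who has only section 14 cannot tell which group is meant. The success threshold is two patients, so the makeup of the denominator and of the first 18 matters. The historical comparison in section 14 (0 of 7 relapse-free, all relapsed within 15 months) is described without any such exclusion.

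**Working it through.** **Inputs, all from section 14.0.** Unpromising rate 1%, promising rate 15%. Two-stage: 18 + 15 = 33, stop if 0 of 18, success at 2 or more. One-stage: 19, success at 2 or more. Stated error rates: alpha 5% in both; power 90% (two-stage) and 80% (one-stage).

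**Step 1. Reproduce the designs with every patient kept.**

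One-stage: P(success) = 1 − (1−p)^19 − 19p(1−p)^18.
- p = 0.01: 0.015.
- p = 0.15: 0.802, matching the stated 80%.

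Two-stage: the trial fails if stage 1 has no success, or if stage 1 has exactly one and stage 2 has none. So P(success) = 1 − (1−p)^18 − 18p(1−p)^32.
- p = 0.01: 1 − 0.8345 − 0.1305 = 0.035.
- p = 0.15: 0.931.

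Both designs meet their stated limits when no patient is dropped.

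**Step 2. Literal reading, excluded failures not replaced.** The number of successes does not change, so neither the stop at zero nor the two-success decision changes. Only the reported rate moves. With three exclusions as an illustration, 2/33 = 6.1% becomes 2/30 = 6.7%, and 2/19 = 10.5% becomes 2/16 = 12.5%.

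**Step 3. Literal reading, excluded failures replaced.** Assume a share c of dosed patients is excluded, all of them failures, and the planned number is refilled. The rate among analysed patients becomes p/(1−c). Putting 0.01/(1−c) into the Step 1 formulas gives the chance of declaring promising at a true 1%:

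| Assumed c | Apparent rate | Two-stage, 33 | One-stage, 19 |
|---|---|---|---|
| 0 | 0.0100 | 0.035 | 0.015 |
| 10% | 0.0111 | 0.042 | 0.019 |
| 20% | 0.0125 | 0.052 | 0.023 |
| 30% | 0.0143 | 0.066 | 0.030 |

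The two-stage cohort passes 0.05 at c of about 18%. The one-stage cohort does so only near 50% (0.055).

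**Step 4. Reading with 9.2.** The excluded patients need not have relapsed. If they had relapsed by two years, Steps 2 and 3 apply. If one of exactly two relapse-free patients is excluded and not replaced, the count falls to one and the result is no longer promising. The bias can go either way, and the documents give nothing from which to size it.

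**Step 5. Set against 12.6.** Under both readings the dropped patient was enrolled and may have received 3F8. If eligible and dosed, that patient has an adequate trial under 12.6 but is missing from the analysis under section 14.

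**The case against.** The strongest reply is that the sentence was never aimed at relapses on study. It refers to the treatment plan, and the CNS patients described there are in remission and leave because of HAMA. Its two clauses follow the order of the two HAMA paragraphs in 9.2. The vocabulary fits too: for progression the protocol has patients come off study (9.2, 13.2, 13.3), while leaving protocol is used in 9.2 only for this HAMA group. A reader might infer from section 14 alone that the plan deletes known failures by design. The documents do not establish that, and the 9.2 reading is plausible.

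It does not settle the wording, however. The 9.2 patients leave for chemotherapy because of HAMA, so the second clause already covers them and the first would add nothing. They receive low-dose maintenance in remission, whereas section 14 speaks of therapy for relapse. The cross-reference follows the HAMA clause and need not govern the first. And the 9.2 reading does not remove the conflict with 12.6.

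Two further objections stand. No replacement rule is written, so the rise in false-positive risk is conditional. And a reader might extend the exclusion to the first-remission cohorts or to Group 1. The sentence is the third bullet under the second-or-later-remission designs, and the CNS text in 9.2 is limited to second or later remission, so the documents do not support the wider scope.

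**Conclusion.** The point holds as a conflict in the analysis population for the two second-or-later-remission cohorts. As worded, the first clause would discard relapse events from a relapse-free analysis, against 12.4 and 12.5. On the alternative reading it is a post-enrolment exclusion with unknown direction of bias. Either way it contradicts 12.6.

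The effect is modest and cannot be fixed from the documents. Without replacement of failures, the decision is unaffected and the reported rate is somewhat too high. With replacement, at assumed shares up to 30%, the two-stage false-positive chance reaches 0.066 against a stated 0.05, and the one-stage chance reaches 0.030, still within its limit. These figures rest on an assumed excluded share, on all excluded patients being failures, and on refilling to the planned number. The point should be corrected, but it does not put the trial's main conclusions in doubt.

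**What to change.** Reconcile section 14 with 9.2 and delete the exclusion. State that:

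- every eligible patient given a first dose of 3F8 stays in the denominator of his or her cohort, including the first 18, the 33 and the 19;
- any CNS relapse after the first 3F8 dose is a relapse event on its date;
- patients enrolled after an earlier CNS relapse, including those who later leave protocol because of HAMA, are counted by their relapse status at two years.

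This changes one sentence in section 14 and alters no treatment or schedule. It does require relapse status at two years for patients who have left protocol. The downside is a slightly less favourable observed rate if the excluded patients were failures.

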15.1 SUBJECT REGISTRATION AND RANDOMIZATION PROCEDURES

15.2 Research Participant Registration

Confirm eligibility as defined in the section entitled Criteria for Patient/Subject Eligibility.

Obtain informed consent, by following procedures defined in section entitled Informed Consent Procedures.

During the registration process registering individuals will be required to complete a protocol specific Eligibility Checklist.

All participants must be registered through the Protocol Participant Registration (PPR) Office at Memorial Sloan-Kettering Cancer Center. PPR is available Monday through Friday from 8:30am – 5:30pm at [contact]. The PPR fax numbers are [contact] and [contact]. Registrations can be phoned in or faxed. The completed signature page of the written consent/verbal script and a completed Eligibility Checklist must be faxed to PPR.

16.1 DATA MANAGEMENT ISSUES

A Research Study Assistant (RSA) will be assigned to the study. The responsibilities of the RSA include project compliance, data collection, abstraction and entry, data reporting, regulatory monitoring, problem resolution and prioritization, and coordinate the activities of the protocol study team.

The data collected for this study will be entered into a secure database. Source documentation will be available to support the computerized patient record.

16.2 Quality Assurance

Weekly registration reports will be generated to monitor patient accruals and completeness of registration data. Routine data quality reports will be generated to assess missing data and inconsistencies. Accrual rates and extent and accuracy of evaluations and follow-up will be monitored periodically throughout the study period and potential problems will be brought to the attention of the study team for discussion and action.

Random-sample data quality and protocol compliance audits will be conducted by the study team, at a minimum of two times per year, more frequently if indicated.

16.3 Data and Safety Monitoring

Institutional monitoring plan for phase I and phase II trials: Memorial Sloan-Kettering Cancer Center (MSKCC) has established standard procedures for data safety monitoring of clinical research (see appendix). For Phase II trials, these procedures include consideration of accrual rates, toxicity, adherence to dose-escalation schedules, adverse event notification and data recording. Therapeutic responses are logged on a central database and approximately 50% are reviewed by an independent committee. An annual report of the trial's progress is sent to the IRB. All of the procedures for Phase II studies outlined in MSKCC's policy are applicable to the current trial and will be followed by the investigators. The analysis of safety will include all patients who receive at least one dose of study medication. Adverse events, including all toxic effects of treatment, will be tabulated individually, and summarized by body system, according to dosage of study medication (single dose as well as cumulative doses of 3F8 and GM-CSF), and according to severity or toxicity grade. Laboratory data will be tabulated and summarized by descriptive statistics, as well as on the basis of MSKCC specified normal ranges.

The policies and procedures for data safety and monitoring of clinical research at Memorial Sloan-Kettering Cancer Center are detailed in Appendix (Data Safety and Monitoring of Clinical Research).

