In our study of 34 patients, consistent with the emergence of an idiotype network, Ab3 (anti-anti-idiotypic) and Ab3' (anti-GD2) response at 6-14 months after treatment with 3F8 alone correlated with improved PFS, and higher Ab3 titers showed a stronger correlation with improved outcome, while non-idiotypic antibody responses (anti-mouse or anti-tumor nuclear antigen) had no apparent impact on outcome.⁵⁶ Since GD2 is an auto-antigen, induced Ab3' response represented a breakdown in self-tolerance. We hypothesized that significant rises in Ab3 or Ab3' would not be possible unless suppressor pathways were removed and naive T or B cells were allowed to repopulate. Following intensive chemotherapy that eliminates a large part of the lymphoid system, exposure to tumor-selective Ab1s (3F8) might induce unique Ab2s that could bias the recovering repertoire towards the GD2 antigen network. The potential for biasing the immune system towards specific antigens has been well documented in murine models⁸⁰ and human disease states.^{81,82} If true, one would expect such an idiotype network to be most successful following intensive immunosuppressive therapy, and not easily induced in immunocompetent patients. In fact, we found that myeloablative therapy suppressed HAMA and Ab2 but was followed by the appearance of Ab3 which in turn correlated with prolonged survival.^{53,56} The prerequisite of strongly immunosuppressive therapy may explain why in most clinical studies of MoAbs, such an idiotype network is not commonly observed. However, when found in patients with colorectal or ovarian carcinoma treated with specific MoAbs, the idiotype network gave patients superior survival advantage.^{54,55,76,77,83-87}

3.11 Isotretinoin (13-cis-retinoic acid) was shown in a randomized national study to decrease the risk of relapse in patients treated in complete remission.⁸ This agent has subsequently become standard of care for NB patients in complete remission. It will be used in this protocol after patients are evaluated for response (and for toxicity) to 3F8/GM-CSF.

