Days 0 and +1: GM-CSF 250 mcg/m²/day, subcutaneously.
3F8 20 mg/m²/day by iv infusion over ~1.5 hr or less (usually 0.5 hr).

Days +2 to +4: GM-CSF 500 mcg/m²/day, subcutaneously.
3F8 20 mg/m²/day by iv infusion over ~1.5 hr or less (usually 0.5 hr).

Note: The daily GM-CSF is not administered if the ANC is >20,000/ul. The ANC count from the previous treatment day will be used to determine whether GM-CSF will be administered or not. If HAMA develops, cycles are deferred until HAMA titer decreases to <1000 Elisa units/ml. Emla cream (lidocaine 2.5% and prilocaine 2.5%) can be used to prevent pain from GM-CSF shots.

9.4 Isotretinoin is administered at 160 mg/m²/d, divided into two doses, x14 days. This treatment can be repeated after a minimum rest period of 14 days, for a total of 6 cycles. It is not taken on the same days as 3F8. All patients receive a minimum of 2 cycles of 3F8/GM-CSF before starting isotretinoin (only to be started after cycle 1 if HAMA develops and precludes timely administration of cycle 2).

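### Section 16.3 summarises adverse events by cumulative dose without defining that dose or its denominator; with 3F8 fixed at one level, the table can show dose trends that do not exist

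*Combined protocol and SAP*

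**What the plan says.** Section 16.3 tabulates adverse events individually and summarises them by body system, by severity or grade, and "according to dosage of study medication (single dose as well as cumulative doses of 3F8 and GM-CSF". On the population it says: "The analysis of safety will include all patients who receive at least one dose of study medication". Patients who stop early are therefore in the table. The section gives no dose bands, no denominator, no adjustment for exposure, and no statement of whether cumulative dose is taken at onset or at the end of treatment.

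The dose schedule is fixed. Section 9.2 states: "The total dosage of 3F8 per cycle is the same as in prior trials (100 mg/m²), administered at 20 mg/m²/day". For GM-CSF, "GM-CSF is dosed at 250 mcg/m²/day from day -5 to day +1", and the daily dose is doubled for days +2 to +4. Section 9.3 omits a day's GM-CSF when the ANC is above 20,000/ul and defers cycles while HAMA is high. In Group 1, the spacing of cycles depends on when marrow CR is reached (9.2).

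Treatment ends early for progression (13.2, 13.3), for "Life-threatening grade 4 toxicity clearly attributable to 3F8" (13.4), or, at the investigator's decision, for other adverse events (13.5).

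On isotretinoin, section 9.4 says "All patients receive a minimum of 2 cycles of 3F8/GM-CSF before starting isotretinoin", with an exception when HAMA holds up cycle 2. Section 3.11 says "It will be used in this protocol after patients are evaluated for response (and for toxicity) to 3F8/GM-CSF".

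**The concern.** A table of adverse events by dose invites the reader to look for a dose effect. Here no dose is assigned at different levels. Patients differ in cumulative 3F8 almost only because they received different numbers of cycles, and that number is partly a consequence of toxicity and of disease course. Two opposite distortions follow. Events that do not stop treatment accumulate in patients who stay on longer, which looks like rising toxicity. Events that stop treatment remove patients from the higher totals, which looks like falling toxicity.

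The single-dose view does not help. 3F8 has one level. The higher GM-CSF dose always falls on the last three 3F8 days, in patients who have just had the lower dose, so dose cannot be separated from day of cycle.

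Co-treatment adds to this. Cycles from the third onward usually come after isotretinoin has started, and section 11.5 lists hepatotoxicity among its effects. Section 3.11 intends toxicity of 3F8/GM-CSF to be evaluated first, but 16.3 does not split the table there.

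At stake is how the safety of the subcutaneous regimen is read. The protocol summary hopes the regimen will become more widely available. A truly cumulative toxicity could be hidden, or one could appear that is not there.

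**Working it through.** **Dose per cycle.** 3F8: 5 days × 20 = 100 mg/m², which reproduces the figure in 9.2. GM-CSF: 7 × 250 + 3 × 500 = 3250 mcg/m². Cumulative 3F8 is thus about 100 × cycles given, apart from missed doses. Cumulative GM-CSF is not a pure cycle count: withholding the last one, two or three days for high ANC gives 2750, 2250 or 1750 mcg/m² (85%, 69%, 54% of 3250).

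**Cycles in 24 months (104 weeks).** Each cycle is counted as 1 week, with 3-week breaks and then 8-week breaks, as in the road maps.
- Group 2: starts at weeks 0, 4, 8, 12, 21, then every 9 weeks to week 102, giving 14 cycles.
- Group 1, CR after cycle 1: starts at weeks 0, 4, 8, 12, 16, 25, then every 9 weeks to week 97, giving 14 cycles.
- Group 1, CR after cycle 3: 15 cycles.
- Group 1, no CR and no progression: starts every 4 weeks from 0 to 100, giving 26 cycles.

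The cycle count therefore depends on response as well as on toxicity and progression.

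**Remaining on treatment.** Take two-year relapse-free survival from section 14 (13% for Group 1, 55% for first CR/VGPR) and assume a constant hazard. The share free of progression at the start of cycle k is S(k) = RFS^(start week/104).
- Group 1 (CR after cycle 1): cycle 5, 0.13^(16/104) = 0.731; cycle 10, 0.13^(61/104) = 0.302.
- Group 2: cycle 5, 0.55^(21/104) = 0.886; cycle 10, 0.55^(66/104) = 0.684.

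**Event risk.** The documents give no figure. Assume a constant 5% per cycle, so there is no true dose effect, and let none, half or all events stop treatment.

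**Reading 1: final total dose, patients as denominator.** If events never stop treatment, a patient with k cycles has had an event with probability 1 − 0.95^k: 5% at k = 1, 19% at 4, 40% at 10, 51% at 14. For the lowest Group 2 band, weight by the share ending at 1, 2, 3 or 4 cycles: (0.0227 × 5.0 + 0.0222 × 9.8 + 0.0217 × 14.3 + 0.0471 × 18.5)/0.1137 = 13%.

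If every event stops treatment, events in the lowest Group 1 band are 0.05 × (1 + 0.95 × 0.925 + 0.95² × 0.855 + 0.95³ × 0.790) = 0.166. The band holds 1 − 0.95⁴ × 0.731 = 0.405 of patients, so 0.166/0.405 = 41%.

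The other cells follow in the same way. Percent of patients with any event at 100–400 / 500–900 / 1000 or more mg/m² of 3F8:

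| Share of events that stop treatment | Group 1 | Group 2 |
|---|---|---|
| None | 11 / 29 / 48 | 13 / 30 / 50 |
| Half | 30 / 27 / 34 | 51 / 44 / 37 |
| All | 41 / 25 / 17 | 65 / 51 / 21 |

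At an assumed 10% per cycle, Group 2 shows 25/51/76 (none) and 80/69/37 (all), and Group 1 shows 22/50/73 and 60/41/31. At 2% the pattern is again a false rise with no stopping and a false fall with full stopping (Group 2, all: 41/29/9; Group 1, all: 21/11/7).

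**Reading 2: dose at onset, all treated patients as denominator.** With no event stopping treatment, the 5% risk appears as 0.05 × S(k). Group 1: 5.0% in cycle 1, 3.7% in cycle 5, 1.5% in cycle 10. Group 2: 5.0%, 4.4%, 3.4%. This is a false fall caused by progression alone.

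**Reading 3: dose at onset, patients at risk as denominator.** The rate is 5% in every band and every scenario, which is the true risk that was put in.

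**The case against.** The strongest reply is that 16.3 does not commit to the harmful version. A single dose can only be attached to an event, so dose reached at onset is at least as natural a reading of cumulative dose, and with patients at risk as denominator it is unbiased. On that view the gap is a missing table specification. The reply adds that:
- the summary is descriptive, with no dose-response test or stopping rule attached;
- the summaries by body system and grade do not depend on the dose split;
- serious adverse event reports record relationship to treatment (17.3);
- isotretinoin is kept off 3F8 days (9.4);
- the institutional monitoring appendix is not among the documents.

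Most of this stands, and it limits the point. It does not remove it: dose at onset without an at-risk denominator still produces a false fall (Reading 2), and 16.3 names no denominator.

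Some stronger readings are tempting and are not supported:
- That the table will show false trends. This depends on choices the text leaves open. With half of events stopping treatment, Group 1 shows hardly any trend (30/27/34).
- That treatment-ending toxicity always falls at low dose. Such an event in cycle 9 sits at 900 mg/m².
- That cumulative dose is nothing but cycles received. This is nearly so for 3F8. Cumulative GM-CSF also varies through the ANC rule, which itself responds to treatment and so adds a second source of confounding.
- That this is the only planned safety summary. It is the only one tied to exposure.

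**Conclusion.** The point holds as a gap in definition with a real but limited consequence. As written, 16.3 permits a table in which toxicity appears to rise or fall with cumulative dose while the risk per cycle is constant. At an assumed 5% per cycle in Group 2, the gap between lowest and highest band runs from +37 percentage points (13% to 50%) to −44 (65% to 21%), depending only on how often events stop treatment.

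These figures rest on assumed event risks (2% to 10%), assumed stopping shares, a constant progression hazard matched to section 14, 3-week early breaks and, for Group 1, CR after cycle 1. HAMA deferrals and missed doses are left out. The figures show what can happen and do not forecast this trial. Mixing of isotretinoin effects into later cycles is possible, but its size cannot be judged from the documents. The efficacy decision rules are unaffected. The change is worth making because it is cheap and gives a readable answer to the exposure question.

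**What to change.** In 16.3, make the exposure-related summary a per-cycle one: for each cycle, patients with the event (by grade) over patients who started that cycle. Show cycles before the first isotretinoin dose separately from later cycles, in line with 3.11.

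If a cumulative-dose view is kept, define it as dose received up to onset, with patients still on treatment at that dose as the denominator. State that 250 versus 500 mcg/m² GM-CSF is not to be read as a dose comparison, because it cannot be separated from day of cycle.

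Leave the summaries by body system and grade as planned. The cost is a rewording in 16.3 and a slightly longer table. It needs event, cycle and isotretinoin start dates, which patient records require anyway, and it changes neither treatment nor sample size.
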